Given the above-mentioned knowledge gaps of healthcare professionals caring for critically ill patients, we propose to conduct a Europewide, descriptive survey for intensive care unit (ICU) clinicians, primarily aimed at addressing the following questions: 1) "How much of ICU everyday practice is palliative care and how is it practiced?"; and 2) "How do clinicians perceive the medico-legal framework around therapy limitations, patient autonomy and prognostication discussions with patients and families?" In addition, this survey will enable us to comparatively assess the perceived extent of ICU palliative care practice in the presence vs. absence of EOL legislation.

METHODS

Study participants and protocol approval

The target population of this descriptive, open survey will include ICU physicians and nurses working in at least 100 ICUs across at least 20 European countries. Each one of participating ICUs will be represented by one or more healthcare

professionals, and the target convenience-sample size will amount to at least 500 respondents (see also below-provided statistical analysis plan). This survey study is part of the European Union-funded Enhancing Palliative Care in ICU (EPIC) project (Proposal number: 101137221; HORIZON-HLTH-2023-DISEASE-03-01). The study protocol will be submitted for approval to the Scientific Council of Evangelismos Hospital, Athens, Greece.

Informed consent and data protection

A similar methodology has been recently described (15). According to the Helsinki declaration, participation in research requires informed consent of the participant. According to Regulation 679/2016 {or General Data Protection regulation (GDPR) of the European Parliament and of the Council, "consent" of the data subject means any freely given, specific, informed and unambiguous indication of the data subject's wishes by which he or she, by a statement or by a clear affirmative action, signifies agreement to the processing of personal data relating to him or her."

Participation in and completion of the current survey means that the participant accepts to share their knowledge on palliative care practice, EOL legislation and EOL practice in their country. The estimated time for survey completion is between 30 and 60 min.

The procedure for "*pseudonymisation*" is detailed below.

A set of 20 consecutive random numbers (range, 10-29) will be generated using "Research Randomizer (www.randomizer.org). Each one of the aforementioned numbers will be assigned to a European country (country code) drawn according to alphabetic order from the list of participating countries. Next to the 2 digits of the country code, a one-to-three-digit number will be placed to represent each participant's temporal order of participation relative to other participants from the same country. The country-specific, temporal order of participants will be determined according to the exact time of submission of the completed study questionnaire. This will form the personal, three-to-five digit code for each study participant.

The survey database will be hosted by the CHARITE Berlin Simulation and Training Centre. Data on questionnaire domains will be stored next to the participant's personal code in Microsoft Excel format. This electronic Masterfile will be stored onto the password-protected hard disk of a personal computer. In addition, next to the participant's personal code, we will enter the following personal data 1) age; 2) gender; 3) religion; 4 and 5) country and center/city of professional activity; 6) characteristics of the participant's ICU (e.g. general, medical, surgical, etc.); 7) the participant's professional focus (e.g. clinical, research, etc.); and 8 and 9) the participant's professional grade (e.g. consultant, professor, etc.) and ICU experience (in years of work). There will be no collection/recording of participants' names or electronic mail addresses. Therefore, the Masterfile will fulfill the criterion of "*pseudonymization*."

Development and testing of the questionnaire

The final version of the questionnaire is presented in the Appendix of the current protocol. The questionnaire was developed based on published, relevant literature (16-23), investigator consensus and comments collected by preliminary testing; the latter comprised administration of the questionnaire to a total of 30 Danish, British and Greek ICU clinicians (10 from each country). Danish and British clinicians were asked to qualitatively assess the readability and understandability of the survey questions and provide comments for improvement as regards content and clarity. Greek clinicians were asked to first respond to the questionnaire, in order to obtain an estimate of the actual time required for survey completion, and subsequently also provide their comments on content and clarity.

In its finalized form, the survey consists of an introduction and 4 sections. The introduction includes core definitions concerning advance directives and shared decision making (16), palliative care (<https://www.who.int/europe/news-room/fact-sheets/item/palliative-care>), treatment limitation (17), active shortening of the dying process (or euthanasia) (17), and family (18). The first section aims at collecting data on participant characteristics, including age, gender, religion, location of professional activity (including hospital name), professional focus, grade and experience. The second section includes questions on patient-level, family-level and healthcare-level domains of palliative care (19-21), as well as participant-rating (5-point scale) of the importance of domain elements; these elements pertain to physical and psychosocial aspects of care, communication, family support and system-level support (19-21). The third section includes questions (and rating by 5-point scale wherever appropriate) about EOL legislation and practices such as and applicability of and clinician-compliance with advance directives, treatment limitation (i.e. withholding or withdrawing of life-sustaining treatments), euthanasia, terminal analgesia/sedation, EOL decision-making and family presence during cardiopulmonary resuscitation (17, 21). Lastly, the fourth section includes 12 questions with two-choice answers (i.e. yes/no) in the context of a recently introduced EOL practice score (17, 22) (with definitions of score subcomponents appended), and an additional 3 general questions about palliative care practice in the participant's ICU.

Internet protocol (IP) address data will be used to ensure the uniqueness of survey participants. More specifically, unlimited, repetitive access to the questionnaire will be allowed from an IP address of a client computer until survey submission. However, following submission of the filled questionnaire through an IP address, will result in discontinuation of survey accessibility through that particular IP address.

Due to the use of snowballing dissemination and sharing of invitation links, it will not be possible to calculate the survey response rate. However, survey completion rate will actually be calculated by dividing the total number of submitted questionnaires to the number of first-survey page visitors. Furthermore, questionnaire completeness rate will be calculated by dividing the number of questionnaires without any missing response to the total number of submitted questionnaires. Missing responses will correspond to questions to which participants will have indicated that they do not wish to answer (see also above). Mutually contradictory responses from participants originating from the same study center, or the same city, or the same country constitute a possibility, especially for the third and fourth section of the survey (15, 17, 22-24). For example, two or more

participants from the same center/city/country may respond differently as regards the legal bindingness of advance directives. In such cases, mutually contradictory responses will be used to estimate the extent of country-specific variation in the perception of law and/or local palliative care practice.

Study outcomes

The primary outcomes will be the absolute numbers of positive (i.e. yes) responses to question groups 10 through 14 of survey section 2, 15 through 23 of section 3, and 24 and 25 of section 4.

Secondary outcomes will include 1) the absolute numbers of positive (i.e. yes) responses to question groups 10 through 14 of section 2 in the presence vs. absence of a positive response to question 24.12 of section 4.

Statistical analysis plan

Statistical analyses will include 1) descriptive statistics; 2) assessment of distribution normality (by Kolmogorov Smirnov test); 3) assessment of European country-/region-level heterogeneity in the responses; and 4) region-level comparisons of responses (17).

We expect to determine substantial heterogeneity in the responses, primarily between northern and southern Europe and central and southern Europe, and generally between countries with high vs low palliative care service integration.

High palliative care score will be defined as presence of at least 16 positive responses (out of 24 possible positive responses) to question groups 10 through 14 of survey section 2.

Generalized estimating equations (GEE) models with robust SEs and exchangeable working correlation structure accounting for the factor center (24) will be applied to examine associations between a high palliative care score, the 9 clinician demographic variables of survey section 1 [with "country" stratified according to "northern, central or southern European region" (17,23,24)], and the EOL practice score and/or its subcomponent EOL practice variables listed in question group 24 of survey section 4. The dependent variable in this analysis will be high palliative care score, yes or no. Reference category for region will be "southern Europe" (17). The maximum number of GEE explanatory variables will be 21. Consequently, our target sample size of 500 participants is expected to result in approximately 24 observations (i.e. response data-points) per variable; this exceeds the recommended threshold of 20 observations per variable (17,23,24,25) by 20% and establishes an adequate safety margin, aimed at addressing the possibility of missing responses.

Significance will be set at two-sided $P < 0.05$. Analyses will be conducted using the latest versions of SSPS or R software.

Expected general benefits from the current study

Survey results will likely serve to refine the EPIC harmonized practice model of palliative care, further clarifying the concepts of primary versus specialist palliative care and ICU clinicians' role in the practice concept. Results from the survey on legal issues are expected to inform stakeholders involved in policy and legislation, and improve security for ICU clinicians in the respective countries and Europewide.

Expected benefits for the conduct of the EPIC trial

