23.1. For adults: is family presence allowed during CPR? Yes, No, Don't know

23.1.1. Importance rating. 1,2,3,4,5

23.2. For children: is family presence allowed during CPR? Yes, No, Don't know

23.2.1. Importance rating. 1,2,3,4,5

23.3. Comments (free text)

24. In your daily practice in ICU, do you have:**24.1. Intensive care unit (ICU) routine family meetings?** Yes, No**24.2. ICU daily deliberation for appropriate level of ICU care?** Yes, No**24.3. ICU end-of-life discussions during weekly meetings?** Yes, No**24.4. ICU written triggers for limitations?** Yes, No**24.5. ICU written end-of-life guidelines?** Yes, No**24.6. ICU end-of-life protocols?** Yes, No**24.7. ICU palliative care specialty consultations?** Yes, No**24.8. ICU ethics consultations?** Yes, No**24.9. ICU staff taking communication courses?** Yes, No**24.10. ICU staff taking Bioethics Courses?** Yes, No**24.11. Country end-of-life guidelines?** Yes, No**24.12. Country end-of-life legislation?** Yes, No**24.13. Any additional comments (free text)**

EOL Practice Variable	Definition
Routine family meetings	Regular (i.e. on admission and at least twice a week) scheduled conferences of at least one member of an ICU patient's family and at least one member of the treating team aimed at a) determining/clarifying the patient's health status, and comorbidities, b) patient values, preferences, and goals concerning treatment options; and c) conveying honest, accurate, and evidence-based information about patient clinical status and current/updated prognosis.
Daily deliberation for appropriate level of care	Routine daily discussions among members of the ICU treating team aimed at confirming that medical/surgical interventions administered to a patient are not disproportionate and/or do not contradict his/her preferences.
EOL discussions during family meetings	Conferences (on admission, and followed up at least as appropriate/feasible) of at least one member of an ICU patient's family and at least one member of the treating team aimed at determining and/or revising/adjusting EOL treatment goals according to the evolution of the patient's clinical course and (particularly changes) of prognosis, and "previously clarified" EOL values/preferences. This variable focuses on a specific type of family meetings' content aimed at achieving consistency between patient wishes and provided EOL care.

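### The secondary comparison by answer to question 24.12 has no adjustment for region, and the GEE that could supply one is not tied to it; if yes answers to 24.12 also differ by region, the contrast is confounded.

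*Combined protocol and SAP*

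**What the plan says.** The introductory paragraph before Methods states that the survey will allow the team to "comparatively assess the perceived extent of ICU palliative care practice in the presence vs. absence of EOL legislation". Study outcomes turns this into one secondary outcome: the numbers of yes answers to question groups 10 to 14, split "in the presence vs. absence of a positive response to question 24.12 of section 4". Item 24.12 in the Appendix asks each respondent for a yes or no on "Country end-of-life legislation".

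The Statistical analysis plan section lists heterogeneity assessment and region-level comparisons as separate items and does not connect them with the 24.12 split. It adds: "We expect to determine substantial heterogeneity in the responses, primarily between northern and southern Europe and central and southern Europe". It then plans a GEE with robust standard errors and an exchangeable structure by centre. The explanatory variables are the nine clinician variables, with country reduced to three regions, and "the EOL practice score and/or its subcomponent EOL practice variables listed in question group 24 of survey section 4". On the outcome of that model it says: "The dependent variable in this analysis will be high palliative care score, yes or no", where high means at least 16 of 24 yes answers.

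**The concern.** A third variable confounds a two-group contrast when it is related both to the outcome and to the grouping. The plan itself predicts the first link, between region and responses. The second is plausible, because 24.12 asks about a national attribute and national attributes can cluster geographically. If both hold, respondents who report legislation and those who do not come from different mixes of regions, and the crude comparison carries the regional difference with it.

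This contrast is the only planned answer to a stated aim. The protocol also expects the survey's results on legal issues to inform policy and legislation. A reader given section 2 practice with and without legislation will tend to read the gap as being about legislation.

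**Working it through.** **The plan's own figures.** Groups 10 to 14 contain 6 + 3 + 6 + 4 + 5 = 24 items, as stated. The maximum of 21 explanatory variables equals 9 clinician variables + 12 components of group 24. 500/21 = 23.8, which matches the stated figure of about 24 per variable. The largest model the plan foresees therefore contains both region and 24.12.

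**What each planned analysis gives for 24.12.**
- Secondary outcome: crude split of the yes-counts, with no region term.
- GEE with the total EOL practice score only: region is included, but 24.12 is absorbed into a 0 to 12 sum and has no coefficient. The and/or wording permits this version alone.
- GEE with the 12 components: 24.12 adjusted for region and for the other 11 components, with the dichotomised score as outcome. It is not named as the analysis of the secondary outcome.

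**Size of the possible bias.** The documents give no regional rates, so every rate below is an assumption. Take three equal regions (south/central/north), no difference by 24.12 inside any region, and a within-region SD of the 24-item count of 4.5. Let a be the share answering yes to 24.12 and p the share of section 2 items answered yes. Then:

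- share in the yes group = Σ(a·p)/Σa
- share in the other group = Σ((1−a)·p)/Σ(1−a)
- spurious difference in items = 24 × (first − second)

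1. Strong aligned gaps: a = 40/70/85%, p = 55/70/75%. Yes group (0.22 + 0.49 + 0.6375)/1.95 = 69.1%. Other group (0.33 + 0.21 + 0.1125)/1.05 = 62.1%. Difference 24 × 0.0696 = **+1.7 items**.
2. Mild aligned gaps: a = 50/65/75%, p = 60/68/72%. 1.282/1.90 = 67.5% and 0.718/1.10 = 65.3%. Difference **+0.5 items**.
3. 24.12 equally common in all regions, p as in 1: both groups have the same regional mix, so the difference is **0**.
4. Shares reversed: a = 85/70/40%, p as in 1. 1.2575/1.95 = 64.5% and 0.7425/1.05 = 70.7%. Difference **−1.5 items**.

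**How often a crude test would call this significant at N=500.** A crude test leaves regional variation in the error, so the SD in each group is √(4.5² + 24² × variance of p among that group's regions). In case 1 this gives 4.85 (n = 325) and 4.93 (n = 175). SE = √(DE × (4.85²/325 + 4.93²/175)) = 0.46 for design effect (DE) 1 and 0.54 for DE 1.4. Then z = 1.67/SE = 3.63 and 3.07, and the rejection rate Φ(z − 1.96) is 95% and 87%. In case 2 (n = 317 and 183, SDs 4.64 and 4.66), SE = 0.43 and 0.51, z = 1.22 and 1.03, giving 23% and 18%.

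**Check on the dichotomised score.** Five further sets of assumed rates, each with a true within-region odds ratio of 1, were run as 4,000 simulated surveys of 500 independent respondents. The crude odds ratio ranged from 0.77 to 2.04. Crude rejection ran from 5%, when 24.12 was equally common in all regions, to 95% under strong alignment. A Mantel-Haenszel analysis stratified by region gave a median odds ratio of 1.00 and rejection of about 5% in all five.

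**The case against.** A reader might infer that a regional difference is bound to show up as an effect of legislation. The documents do not support that. They predict heterogeneity in the responses generally, but nowhere say how answers to 24.12 are distributed over the three regions. A national attribute need not line up with a north/central/south split. Cases 3 and 4 show that the bias can be nil or negative. This objection stands, and the point is conditional for that reason.

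A reader might also infer that the GEE cannot help. That is too strong: its component version gives a region-adjusted coefficient for 24.12 on a score built from the same 24 items. What remains is that this version is optional and not assigned to the secondary outcome.

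One could object to the component version because guidelines and protocols may follow from legislation, so adjusting for them removes part of the contrast. That causal path is an assumption. These items could equally share a common cause with legislation, so leaving them out is a modelling choice.

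Finally, the survey is descriptive, its aim concerns perceived practice, and it claims no causal effect. The outcome is defined as absolute numbers with no test named, so the rejection rates above assume a test that the plan does not specify. Both remarks are fair. They lower the severity but do not remove the gap: the contrast answers a stated aim, and its planned form ignores a factor that the plan itself expects to matter.

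**Conclusion.** The concern holds in conditional form. The 24.12 contrast has no specified adjustment for region, and the model that could provide it is neither linked to this outcome nor required to contain 24.12 as a separate term. Whether confounding occurs, and in which direction, depends on the regional distribution of 24.12, which the documents do not give.

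The sizes, from +1.7 through 0 to −1.5 of 24 items, are illustrations. They rest on assumed regional rates, equal regions, an assumed within-region SD of 4.5 and no within-region effect. The significance rates also assume a design effect between 1 and 1.4. None of this shows that the published difference would be spurious, only that the planned comparison could not tell. It is a cheap improvement, not a flaw that invalidates the survey.

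**What to change.** In the Statistical analysis plan, name the analysis of the secondary outcome:

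- a GEE with the centre clustering already planned;
- the section 2 yes-count or proportion as outcome;
- 24.12 as its own term;
- adjustment for region and the clinician variables already collected.

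Report the crude split beside it, labelled descriptive. A version that also includes the other group 24 items can serve as a sensitivity analysis.

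State two limits in advance. Three broad regions leave country-level confounding, since legislation is a country attribute. And if 24.12 hardly varies within region, legislation and region cannot be separated, and the report should say so. Additional protocol features anticipates contradictory answers within a country, so some within-region variation may exist.

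The cost is a few lines of SAP text, one extra model and a wider interval for the 24.12 contrast. No new data are needed.

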6.1 General/mixed, Medical, Surgical, Other

6.2 University-affiliated, Not University-affiliated

6.3 Number of ICU beds (number)

7. Your professional focus (please choose all that apply)

Clinical, Education, Research, Management, Other (please specify)

8. Your grade (please choose all that apply)

Nurse, Trainee / non-specialist, Consultant / specialist,

University-related (Lecturer/Professor), Other (please specify)

9. Your professional intensive care experience

Less than 5 years, 5 to less than 10 years, 10 to 20 years, More than 20 years

Perceptions about provision of care for end of life / treatment limitation decisions

Please use the following 5-point scale to rate the level of importance (regarding routine/usual/standard practice) of the following domains of end-of-life patient care. Please note that the term "importance" corresponds to what the clinician considers as important for the care of ICU patients who are nearing end-of-life and have a documented poor prognosis.

1=unimportant
 2=low importance
 3=average importance
 4=high importance
 5=maximum importance

At the end of each domain, it is possible to clarify your responses and/or add other comments

10. Physical aspects of care

10.1. The patient's pain is assessed at least once daily, depending on their individual needs

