10.1.1. Is this part of your routine practice? Yes, No, Don't know

10.1.2. Importance rating. 1,2,3,4,5

10.2. Pain relief is part of the daily ward round goals

10.2.1. Is this part of your routine practice? Yes, No, Don't know

10.2.2. Importance rating. 1,2,3,4,5

10.3. The patient's breathing/dyspnea is assessed at least once daily, depending on their individual needs

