13.5. Comments (free text)

14. System-level multidisciplinary support

14.1. Is there effective cooperation among members of the treating team? Yes, No, Don't know

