14.1.1. Importance rating. 1,2,3,4,5

14.2. Do you think that end-of-life decisions should include an interdisciplinary team of healthcare professionals? Yes, No, Don't know

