14.2.1. Importance rating. 1,2,3,4,5

14.3. Do you think that end-of-life decisions should include the patient (if feasible)?

Yes, No, Don't know

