14.3.1. Importance rating. 1,2,3,4,5

14.4. Do you think that end-of-life decisions should include the family? Yes, No,

Don't know

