14.4.1. Importance rating. 1,2,3,4,5

14.5. Do you think that end-of-life decisions should include others? Yes, No, Don't know

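### The only GEE outcome, high palliative care score, adds four opinion items (14.2–14.5) to 20 practice or status items, so the model cannot show whether an association concerns practice or views

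*Combined protocol and SAP*

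**What the plan says.** The Statistical analysis plan defines one dependent variable for the GEE models: "High palliative care score will be defined as presence of at least 16 positive responses (out of 24 possible positive responses") to question groups 10 to 14 of survey section 2. The explanatory variables are the nine demographic variables, with country grouped into three regions and southern Europe as reference, and the EOL practice score and/or its components.

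The Appendix shows what the score counts:

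- Each item in groups 10 to 13 asks: "Is this part of your routine practice? Yes, No, Don't know".
- Item 14.1 asks: "Is there effective cooperation among members of the treating team"?
- Item 14.2 asks: "Do you think that end-of-life decisions should include an interdisciplinary team of healthcare professionals"?
- Item 14.3 asks: "Do you think that end-of-life decisions should include the patient (if feasible")?
- Item 14.4 asks: "Do you think that end-of-life decisions should include the family"?
- Item 14.5 asks: "Do you think that end-of-life decisions should include others"?

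Section 2 of the questionnaire is headed "Perceptions about provision of care for end of life / treatment limitation decisions". The aims paragraph before Methods asks how much of everyday ICU work is palliative care and how it is practised, and wants to compare the perceived extent of that practice with and without EOL legislation. No score or model that leaves out 14.2–14.5 is described.

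**The concern.** A yes to any of 14.2–14.5 records what the respondent thinks ought to happen, yet it earns the same point as a yes about what the unit routinely does. The questionnaire itself draws this distinction: 12.5 and 12.6 ask whether involving the patient and the family in end-of-life decisions is routine practice, while 14.3 and 14.4 ask whether they should be included.

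Region and religion are explanatory variables, and views on who should decide may vary with both. The plan itself expects marked north–south and central–south differences in the responses. If views differ and practice does not, the model can still show an association with a high score. A reader who takes that score as a measure of practice would then draw the wrong conclusion from the study's only association model.

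**Working it through.** **Reproducing the 24.** Yes/no items per group, counted in the Appendix: group 10 has 6, group 11 has 3, group 12 has 6, group 13 has 4 and group 14 has 5. 6 + 3 + 6 + 4 + 5 = 24, which agrees with the plan. Without 14.2–14.5 the count is 20 (19 routine-practice items plus 14.1), so the stated 24 is reached only by counting the opinion items.

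**How far opinions move the bar.** Practice or status yeses needed = 16 − (opinion yeses). This needs no assumption.

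| Opinion yeses | Needed of 20 | Per cent |
|---|---|---|
| 4 | 12 | 60 |
| 3 | 13 | 65 |
| 2 | 14 | 70 |
| 1 | 15 | 75 |
| 0 | 16 | 80 |

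For a respondent with 12 to 15 practice or status yeses, the opinion answers settle the classification.

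**What this could do to an odds ratio.** The documents give no yes-rates, so everything from here is assumed. Take two regions with the same practice: the number of yeses among the 20 items is beta-binomial with mean yes-rate p (0.60 to 0.75) and within-person correlation ρ (0.1 to 0.2). Opinion items are independent, with these yes-rates for 14.2/14.3/14.4/14.5:

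- Only 14.5 differs: 0.98/0.98/0.98/0.50 against 0.98/0.98/0.98/0.30.
- Mild contrast: 0.95/0.95/0.95/0.50 against 0.90/0.90/0.85/0.30.
- Strong contrast: 0.95/0.95/0.95/0.50 against 0.80/0.70/0.50/0.10.

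Formula: P(high) = Σ over k of P(k opinion yeses) × P(practice yeses ≥ 16 − k).

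Worked case, mild contrast, p = 0.65, ρ = 0.1. The beta parameters are 0.65 × 9 = 5.85 and 0.35 × 9 = 3.15. P(practice yeses ≥ 12, 13, 14, 15, 16) = 0.671, 0.579, 0.478, 0.374, 0.274.

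- First region: shares facing bars 12 to 16 are 0.429, 0.496, 0.071, 0.004, 0.000. P(high) = 0.288 + 0.287 + 0.034 + 0.001 = 0.610.
- Second region: shares are 0.207, 0.564, 0.203, 0.025, 0.001. P(high) = 0.139 + 0.327 + 0.097 + 0.009 + 0.000 = 0.572.
- Odds ratio = (0.610/0.390)/(0.572/0.428) = 1.17; difference 3.9 points before rounding.

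Over all p and ρ in the stated ranges:

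| Opinion contrast | Odds ratio for high | Difference in % high |
|---|---|---|
| None | 1.0 | 0 |
| Only 14.5 differs | 1.06–1.09 | 1–2 points |
| Mild | 1.12–1.19 | 2–4 points |
| Strong (upper illustration) | 1.43–1.71 | 7–12 points |

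If 14.2–14.4 are nearly always answered yes (0.98 each), about 96–97% of respondents face a bar of 12 or 13, a spread of one item. At practice yes-rates of 0.85 to 0.90 the differences fall to at most 0.6, 1.4 and 5 points for the three contrasts, although the odds ratios do not shrink. These are unadjusted two-group figures, not results of the planned GEE.

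**The case against.** The strongest defence is that the composite is what the study set out to measure. The questionnaire presents itself as a survey of perceptions, section 2 carries that word in its heading, system-level support is one of its declared domains, and the plan calls the outcome a palliative care score, not a practice score. This stands against any reading of the 24 as a counting error: the number matches the Appendix exactly. It does not remove the difficulty that the aims ask about practice and the items themselves distinguish practice from opinion.

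A second defence is that the plan already includes descriptive statistics and region-level comparisons of responses. A reader might infer that the planned analyses as a whole cannot tell practice from views; the documents do not support that. If those comparisons are reported by item, they will show whether 14.2–14.5 differ by region. They cannot show whether an adjusted, centre-clustered association survives without those items.

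Third, a reader might infer an inflated false-positive rate. That does not follow either. If opinions differ between regions, the 24-item score as defined truly differs, and rejecting the null is correct for that outcome.

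Fourth, large effects need either a strong opinion contrast, which nothing in the documents supports, or independence of 20 related answers from one person, which is implausible. This stands, and the conclusion does not rest on either.

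**Conclusion.** The point holds as a limit on interpretation. It is certain that four of the 24 items are opinions, that they can supply up to 4 of the 16 points needed, and that the practice bar moves between 12 and 16 of 20. It is also certain that the GEE model as planned cannot attribute an association with region, religion or the EOL practice score to practice rather than views.

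The size is uncertain and probably modest. It rests on assumed yes-rates, equal practice in the two regions compared, and a within-person correlation of 0.1 to 0.2. On those terms opinions alone shift the odds ratio by under 10% if only 14.5 differs and by 12–19% for a mild contrast. The shift is larger only if opinions differ strongly, and absent if they do not differ.

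Severity is minor to moderate. The descriptive primary outcomes are not affected.

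**What to change.** Keep the 16-of-24 definition and add to the Statistical analysis plan:

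> As a prespecified sensitivity analysis the GEE model will be refitted with a score from the 20 items 10.1.1–13.4.1 and 14.1 (high = at least 14 of 20; 13 of 20 shown as a check, since two-thirds of 20 is 13.3). Items 14.2–14.5 will be reported separately as views. The 24-item score will be described as a composite of reported practice and views. An association will be interpreted as one with practice only if it is similar in direction and size for the 20-item score at the 14-of-20 cut.

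Fixing the cut in advance matters because 16/24 = 66.7% has no exact match on 20 items: 14/20 is 70% and 13/20 is 65%. Tying the interpretation to the 14-of-20 cut settles what happens if the two disagree.

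The cost is a few lines of text and one or two extra model fits on data already being collected, with no change to the questionnaire or sample size. There are two drawbacks. The cut cannot equal the original proportion. Item 14.1 is an evaluation of teamwork without the routine-practice wording, and it would be the only system-level item left in the 20-item score.
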